Neuroimaging Component. Given the severe negative outcomes associated with co-occurring AUD and PTSD and lack of effective treatments, investigation of the neural circuitry and neurochemistry underlying AUD/PTSD and involved in positive therapeutic response to NAC could be important in guiding future studies targeting this circuitry using other therapeutic agents or treatment modalities. To that end, fMRI and ¹H-MRS data will be acquired at baseline and end of treatment on all fMRI-eligible participants to examine (a) glutamate concentrations, (b) resting state connectivity, and (c) response to alcohol, trauma, and neutral cues. Scans will be conducted at the MUSC Center for Biomedical Imaging (see Facilities and Resources section), which houses a Siemens 3T TIM Trio MRI scanner (Siemens Medical, Germany). The neuroimaging component will involve three visits, each lasting 60-90 minutes. During visit 1 (baseline screening visit), we will develop the personalized imagery scripts for trauma and/or racial-based trauma, alcohol and neutral cues. During visit 2 (Randomization Visit, prior to medication initiation) and visit 3 (Post Treatment – 8 Visit), we will conduct the fMRI and ¹H-MRS scanning procedures. Women of childbearing age will receive a urine pregnancy test before each MRI. Imagery scripts will be developed according to standardized procedures⁴¹ and employed in our ongoing research (see Preliminary Studies section). The Wk 8 scan will be conducted approximately one hour post-NAC administration to ensure findings reflect effects of NAC¹²²⁻¹²³. Participants will be screened for metal using a handheld metal detector. Trained staff will position subjects on the scanner bed with foam padding placed around their head to prevent motion. Participants will wear headphones to listen to the audio-recorded scripts. During initial scanner tuning, localizing, and structural

Overview of neuroimaging session. Assessment of (a) ACC glutamate, (b) resting connectivity, and (c) response to alcohol, trauma and neutral cues.

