N=150). In the same pilot trial, 77% of subjects completed the 8 week trial; we anticipate similar retention in the proposed study. Thus, a randomized sample size of 100 participants per treatment arm (total N=200) would maintain power to detect the clinically significant difference stated above in the presence of ~25% attrition during the study. Similarly, in the same pilot study, reductions in craving were significantly greater in the NAC vs. placebo treated group ($\Delta=3.0$ vs. $\Delta=1.3$). The randomized sample size of 100 per treatment arm provides >95% power with a type 1 error rate of 5% to detect this effect in the presence of 25% attrition during the study period. It is hypothesized that NAC reduces the risk of drinking as compared to placebo. With this stated sample size, a 25% decreased risk in the consumption of standard drinks can be detected with at least 80% power between the NAC and placebo treated arms (Risk Ratio=0.75).

Power calculations for the neuroimaging component are based on previous studies of individuals with PTSD or substance use disorders. Based on our previous work and the extant literature, we conservatively estimate ~70% of participants (140/200) will be eligible and volunteer for the neuroimaging component. A recent study of 29 individuals (PTSD=14, controls=15) observed significant differences in PFC-AMY resting state connectivity⁵⁰. The effect size for this difference was 0.8 (Cohen's d). Thus, power (1- β) reaches .80 with a total sample size of N=26 (two-tailed, alpha=.05). Another study of 45 cocaine-dependent individuals found that individuals who relapsed (n=24) had significantly lower PFC-AMY connectivity at baseline as compared to individuals who did not relapse (n=21)⁴⁹. The effect size for this reduction was 1.0. Thus, power (1- β) reaches .80 with N=34 subjects (two-tailed, alpha=.05). For exploratory hypothesis 4, the only published study of NAC effects on brain glutamate found that one dose of NAC vs. placebo administered 1 hour prior to scanning, led to a significant modification in ACC glutamate with an effect size of $d = 2.6$ in individuals with cocaine dependence. Although the present study will be examining the effects of chronic NAC treatment in individuals with AUD and PTSD, an effect of similar magnitude would provide power > 0.99. The present study is therefore well-powered to test the proposed hypotheses.

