Hypothesis 2: NAC treatment will result in significantly greater reduction in PTSD severity as compared to placebo. To test this hypothesis, generalized linear mixed effects regression models with a Gaussian distribution will be developed to assess group differences while adjusting for baseline CAPS-5 scores. Assumptions of residual normality and homoscedasticity will be checked using statistical test and graphical methods (Residual and Q-Q plots, and Shapiro-Wilk tests) and transformation will be done as necessary. Restricted maximum likelihood (REML) methods will be used to estimate the fixed effects and variance components.

Hypothesis 3A: Prefrontal cortex-amygdala connectivity at rest and in response to alcohol vs. neutral cues will predict reduction in alcohol use severity (total standard drinks).

Hypothesis 3B: Prefrontal cortex-amygdala connectivity at rest and in response to trauma vs. neutral cues will predict reduction in PTSD severity (CAPS-5).

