For hypotheses 3A and 3B, the following preprocessing and analytical parameters will be used. Preprocessing: Post-acquisition preprocessing and statistical analysis of imaging data will be performed using FEAT (FMRI Expert Analysis Tool) Version 5.98, part of FSL (FMRIB's Software Library). Data will be preprocessed using scripting tools from FEAT. Non-brain signal will be removed using FSL's BET brain extraction. Scans will be corrected for motion using FSL's linear registration and scans will be spatially smoothed using a Gaussian kernel of 8 mm FWHM. Participants with head motion ≥ 0.2 mm will be excluded from the analyses¹²⁷. Motion artifacts will be identified and scrubbed from each subject's data. Scans will be spatially co-registered with a standardized anatomical template (Montreal Neurological Institute) using a 12 parameter affine transformation. Analysis: Functional connectivity will be measured using a psychophysiologic interaction seed-based approach¹²⁹⁻¹³⁰. PPI analysis is used to assess the functional coupling between different brain regions. The PPI is defined as the change in connectivity of one area (i.e., the seed region) to another in relation to the experimental context (e.g., alcohol vs. neutral cues). PPI analyses for resting state, trauma and alcohol cues will be performed separately. Customized sq. wave forms representing the trauma run (1=trauma block and -1=neutral block) and the alcohol cue run (1=alcohol block and -1=neutral block) the duration of each block will be convolved with a double-gamma hemodynamic response function. A mask of the seed region will be made using a 12-mm diameter sphere located in the center of the AMY using the MNI coordinates (x, y, z = ± 22 , 0, -22). The transformation parameters described above will also be applied to the mask. For each subject, the mean corrected and high pass filtered time series of the BOLD signal in the AMY will be extracted and used in a single subject whole brain PPI analysis. The PPI model will include the task vector, time series of the BOLD signal in the AMY, a term representing the positive task x seed interaction, and a term representing the negative task x seed interaction. The first level analysis will generate contrast images of the parameter estimates for each of the four regressors. Voxels will be thresholded at $Z > 2.3$ using a corrected cluster threshold of $p = 0.05$. The contrast images of the parameter estimates of the positive and negative task x seed interactions will be combined for group-level t-tests to identify regions that exhibited altered connectivity with the AMY during the trauma and alcohol cues as compared to neutral cues. All group-level results will be thresholded at $Z > 2.3$ using a corrected cluster threshold of $p = 0.05$. Separate linear regression tests will be used to test for associations between PFC-AMY connectivity at baseline and improvement in AUD and PTSD symptoms during treatment. Changes in total standard drinks will be regressed against the parameter estimate obtained from the center voxel from each cluster that exhibited a significant task x seed interaction with the AMY at rest and in response to the alcohol cues (Hypothesis 3A). Changes in CAPS-5 total scores will be regressed against the parameter estimate obtained from the center voxel from each cluster that exhibited a significant task x seed interaction with the AMY at rest and in response to the trauma cue (Hypothesis 3B). Further exploratory analyses will examine change in PFC-AMY connectivity from pre- to post-treatment and associations with alcohol and PTSD outcomes, both within and between medication groups.

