
Exploratory Hypothesis 4: NAC treatment will be associated with a significant change in ACC glutamate concentrations, as compared to placebo. Change in ACC glutamate concentrations will be associated with alcohol and PTSD outcomes.

Analysis of PRESS data will be conducted using LC Model 6.3¹³¹, an operator-independent curve-fitting software package that uses least-squares estimation for quantifying metabolite concentrations; the basis set for TE = 40ms is provided by the vendor and includes a number of metabolites including glutamate, creatine, glutamine, N-acetylaspartate, and phosphocholine. Only metabolites with fitting uncertainties (Cramer-Rao Lower Bound values) $< 20\%$ of SD in the LC Model output will be retained for analysis. LC Model includes standardized zero filling, Fourier transformation, and automated phase, baseline and eddy current correction. To address variability in within-voxel tissue composition we will extract and segment T₁-weighted images into partial volume maps of gray matter (GM), white matter (WM), and CSF using FSL tools, match the coordinates and size of the ¹H-MRS voxel with the segmented images and extract the tissue fractions within the voxel, correct the raw values obtained from the LC model (scaled

to water) for CSF and coil loading, and calculate each participant's GM to brain matter (GM/[GM+WM]) ratio for use as a covariate in the analyses. Change in glutamate levels will be analyzed as a mixed model (SAS PROC MIXED) with time as a within subject variable and medication group as between subject variables. Variables known to influence ACC glutamate levels (e.g., age, smoking status, tissue composition) will be considered as covariates. Further exploratory regression analyses will examine associations between glutamate difference scores and clinical outcomes (e.g., change in total standard drinks and CAPS-5 score) both within and between medication groups.

Summary: The proposed study will answer important questions regarding the potential of NAC as an effective pharmacotherapy for AUD and comorbid PTSD, and elucidate possible mechanisms underlying improved outcomes. The findings from this study have the potential to significantly improve the standard of patient care and accelerate research on the treatment of AUD and co-occurring PTSD

REFERENCES

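### On its natural reading, the Hypothesis 4 glutamate model compares mean change between arms and gives up precision that adjusting for the pre-medication scan would supply

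*Combined protocol and SAP*

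**What the plan says.** The hypothesis, in the Statistical Analyses under Exploratory Hypothesis 4, is that "NAC treatment will be associated with a significant change in ACC glutamate concentrations, as compared to placebo". The analysis follows in the same section: "Change in glutamate levels will be analyzed as a mixed model (SAS PROC MIXED) with time as a within subject variable and medication group", the latter as the between-subject factor. On covariates it says: "Variables known to influence ACC glutamate levels (e.g., age, smoking status, tissue composition) will be considered as covariates". Baseline glutamate is not in that list, and nothing says that the two arms share a baseline mean.

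The Neuroimaging Component section fixes the number of time points at two: "data will be acquired at baseline and end of treatment on all fMRI-eligible participants". The first scan precedes study drug: "During visit 2 (Randomization Visit, prior to medication initiation".

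Elsewhere the plan does adjust for baseline. Hypothesis 2 compares the arms "while adjusting for baseline CAPS-5 scores", and Hypothesis 1 puts baseline drinking and craving into its models. The covariate rule under General is tied to the primary outcomes, so it does not bring baseline glutamate into the Hypothesis 4 model.

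**The concern.** When a mixed model has two time points and each arm has its own free mean at both, the time-by-group term is the difference between arms in mean change. But the first scan is taken before medication, so randomisation already makes the true baseline means equal, and a model with free baseline means does not use that fact. Any chance gap between the arms at the first scan is subtracted in full, although only a fraction (about rho, if the variances are equal) is expected to persist to the second scan. The rest is added noise.

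What is at stake is the standard error of the one randomised test of whether NAC alters ACC glutamate, in a sub-study of volunteers. No primary outcome is touched. The data needed to do better are already being collected.

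**Working it through.** **Inputs from the documents.** Two scans, the first before medication (Neuroimaging Component). Imaging sample: "we conservatively estimate ~70% of participants (140/200) will be eligible and volunteer for the neuroimaging component", so about 70 per arm at equal allocation. Effect size d = 2.6, stated power above 0.99, and trial attrition of about 25% (Power and Sample Size).

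**Assumptions.** Equal variance sigma² at both scans; correlation rho between scans, shown over a range; two-sided alpha 0.05, which the plan states for the connectivity comparisons but not for Hypothesis 4. The 25% attrition is a trial-wide figure, applied to imaging only as a sensitivity case.

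**Step 1: the plan's own figure.** At d = 2.6, 70 per arm gives power 1.000, and so does 52 per arm. Seven per arm already gives 0.994 (noncentral t). The statement of power above 0.99 reproduces.

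**Step 2: what the planned contrast is.** In one simulated data set (70 per arm, rho 0.6), the mixed-model time-by-group estimate was 0.1045 (SE 0.1403). The difference in mean change was 0.1045 (SE 0.1403), the same quantity.

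**Step 3: complete data, n per arm.**
- Change contrast: variance = (2 sigma²/n) × 2(1 - rho).
- Baseline-adjusted contrast: variance = (2 sigma²/n) × (1 - rho²).
- Ratio, adjusted to change = (1 + rho)/2, so the cut is (1 - rho)/2.

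With unequal SDs s0 (first scan) and s1 (second scan), the gap between the two variances is proportional to (s0 - rho × s1)². This is never negative, so in large samples adjustment does not lose.

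**Step 4: 25% of second scans missing at random, unrelated to glutamate.** The planned likelihood model still uses the first scans of people without a second.
- Planned contrast: (2 sigma²/n) × [(1 - rho²)/0.75 + (1 - rho)²].
- Adjusted contrast: (2 sigma²/n) × (1 - rho²)/0.75.

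Example at rho 0.5: 0.75/0.75 = 1.00 against 1.00 + 0.25 = 1.25. The ratio is 0.80, a cut of 20%.

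| rho | Cut, complete data | Cut, 25% missing (formula) | Cut, 25% missing (simulated) |
|---|---|---|---|
| 0.3 | 35% | 29% | 27% |
| 0.5 | 25% | 20% | 20% |
| 0.7 | 15% | 12% | 11% |
| 0.9 | 5% | 4% | 3% |

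Simulations of 6000 replicates per rho gave complete-data ratios of 0.67, 0.76, 0.85 and 0.95, against 0.65, 0.75, 0.85 and 0.95 from the formula.

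**Step 5: in terms of power (70 per arm, complete data).** The smallest effect detectable with 80% power, in SDs of one scan, is 2.80 × sqrt(V × 2/70), where V is 2(1 - rho) or (1 - rho²).

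| rho | Change contrast | Adjusted contrast | Adjusted power where change has 80% |
|---|---|---|---|
| 0.3 | 0.560 | 0.452 | 93.5% |
| 0.5 | 0.474 | 0.410 | 89.9% |
| 0.7 | 0.367 | 0.338 | 86.0% |
| 0.9 | 0.212 | 0.206 | 82.0% |

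At rho 0.5, 70 per arm with adjustment is worth 70/0.75, or about 93 per arm, without it. In the missing-data case the factor is 1/0.80 = 1.25 rather than 1.33. At d = 2.6, power stays above 0.99 under either model.

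**The case against.** The strongest reply is that the plan's wording is open. It does not name the time-by-group term, the treatment of the baseline means or the covariance structure, and its covariate list is only illustrative. A mixed model with a common baseline mean would fit the same sentence. This stands to the extent that the reading here is the natural one and not an explicit one. It does not remove the point: an analyst following the text as written would most likely fit free baseline means, and if baseline adjustment was intended, the plan should say so.

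Second, the hypothesis is exploratory, the planned contrast is valid, and the stated power is above 0.99. All true. But that power rests on d = 2.6 from a single dose in cocaine dependence, and the Power and Sample Size section itself notes that this trial studies chronic treatment in a different population.

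Third, the planned mixed model already keeps people who miss the second scan. This also stands. It narrows the gain (Step 4) and means that retaining those people is not an advantage over the plan.

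A reader might also infer that the analysis of connectivity change, under Hypotheses 3A and 3B, shares the weakness: "Further exploratory analyses will examine change in PFC-AMY connectivity from pre- to post-treatment". The documents do not support that. They give no between-arm model and no covariates for it, so no loss of precision can be attributed to it.

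**Conclusion.** The point holds for exploratory Hypothesis 4 only, as a loss of precision on the natural reading of the model. The variance cut available is (1 - rho)/2 with complete data, from 35% at rho 0.3 to 5% at rho 0.9. It is about 29% down to 3-4% if a quarter of second scans are missing at random. These figures rest on equal variances at the two scans and on a correlation that the documents do not give; as rho nears 1 the gain vanishes.

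Three stronger inferences are not supported. The planned contrast is not biased. The sub-study is not shown to be underpowered: the stated power reproduces and is the same under either model, so precision becomes important only if the true effect is much smaller than d = 2.6. And the sample size is not capped at 140 or known to fall to 105. The plan calls 140 a conservative estimate, and 140 × 0.75 = 105 borrows the trial-wide attrition for a second scan that the protocol places at end of treatment in one sentence and at Week 8 in others.

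**What to change.** State the baseline handling in the Hypothesis 4 analysis. Preferred: fit the planned PROC MIXED model with both scans as outcomes and one common pre-medication mean for both arms (a constrained longitudinal model). In practice, replace the free group effect at the first scan by a single indicator for NAC at the second scan, whose coefficient is the treatment contrast. Keep the grey-matter ratio, age and smoking covariates. This retains people with only a first scan, as the present model does.

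Alternative: model second-scan glutamate with baseline glutamate as a covariate, plus the same other covariates, and say that people without a second scan are dropped.

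The cost is one sentence in the plan and one changed model statement, with no new data or visits. It should be settled before unblinding.
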